1 PROTOCOL SUMMARY

1.1 SYNOPSIS

Title:	Telehealth high intensity interval exercise and cardiometabolic health in spinal cord injury
Study Description:	This study will determine if the implementation of a home-based telehealth high intensity interval exercise-training (HIIT) program can significantly improve cardiometabolic health and physical function in a cohort of individuals with longstanding spinal cord injury (SCI). Results from this study will determine feasibility, overall enjoyment, and health impact of implementing a home-based telehealth HIIT program in individuals with SCI.
Objectives:	The goal of this study is to integrate a home-based telehealth HIIT arm crank exercise training program in individuals with SCI and assess changes in cardiometabolic health and physical function. The secondary goal is to explore the uptake and implementation of HIIT in SCI.
Study Population:	
 1. Individuals 19-65 years old with confirmed diagnosis of traumatic SCI at the cervical or thoracic level (C7-T12), classified as A, B, C, or D (motor and sensory complete or incomplete) on the AIS scale. 2. At least 6 months post-injury.
Phase:	Not Applicable
Description of Study Intervention:	
 • HIIT training will be delivered two times per week for 16 weeks (32 sessions). Each session will be separated by at least 24-hrs. Participants will be allowed to choose the days and times that they feel exercise will fit into their schedule. The HIIT protocol will be determined based on peak anaerobic power measures during an arm crank Wingate Cycle test. HIIT will consist of 20 minutes of exercise consisting of four minutes of arm crank exercise at 5% of peak anaerobic power followed by 30 seconds at 30% of the peak anaerobic power; this cycle will be repeated four times, ending with two minutes of recovery at 5% of peak anaerobic power. • Other: No-exercise control group 
 ○ No-exercise control group
Study Duration:	3 years
Subject Duration:	6 months

INTRODUCTION

1.2 STUDY RATIONALE

For individuals with spinal cord injury (SCI), exercise participation reduces the risk of developing chronic cardiometabolic diseases, which are leading causes of rehospitalization and death within this population. Accordingly, recent SCI exercise guidelines have highlighted a need for exercise trials that can improve cardiometabolic factors such as glucose tolerance, blood lipids, blood pressure, and body composition. However, to date, the number of exercise trials examining these cardiometabolic outcomes in SCI is low, and these exercise regimens are often inconvenient for individuals with SCI to perform within their community. In addition to the functional impairment associated with the disability, individuals with SCI experience a number of barriers to exercise participation, such as lack of time (e.g. conflict with work schedule), accessible or usable equipment and facilities, and transportation. Thus, it is important to identify effective modes of exercise that can improve overall health but do not require a significant overall weekly time commitment. Investigators recently demonstrated that individuals with SCI could safely perform high intensity interval training (HIIT) using arm crank cycling and that as few as two days per week of HIIT could improve cardiometabolic health. Despite the advantages of HIIT, it is important to identify methods of implementing exercise trials that can successfully reach and maintain participation in larger cohorts. Recent work by the investigative group demonstrated that individuals with SCI expressed favorable perceptions of home-exercise training that incorporated telehealth technology, which allowed a fitness specialist to remotely monitor participants' training progress in real-time and provide verbal support via videoconferencing. This method of training holds even greater value for home-exercise programs that require monitoring to dose-specific protocols such as HIIT. However, the long-term success of HIIT will greatly depend on the ease at which the program can be implemented, as well as participants' adherence and perceptions of using the technology, which has not been investigated in SCI. The goal of this study is to integrate a home-based telehealth HIIT arm crank exercise training program in individuals with SCI and assess changes in cardiometabolic health and physical function. The secondary goal is to explore the uptake and implementation of HIIT in SCI. 40 participants will be randomized to home-based HIIT exercise or a no-exercise control group for 16-weeks. Body composition, aerobic fitness, muscular strength, and changes in cardiometabolic health will be assessed at baseline and 16-weeks post training. In addition to changes in cardiometabolic health outcomes, the investigators will also conduct interviews with participants to determine overall perceptions of the program, program likes and dislikes, perceived satisfaction and value, usability of equipment and technology, and factors that influence adherence.

2 STUDY DESIGN

2.1 OVERALL DESIGN

Primary Purpose : Prevention

Allocation : Randomized

Interventional Model : Parallel Assignment

Interventional Model Description: In a longitudinal study design, 40 participants with chronic SCI will be randomly assigned to one of the two study groups (HIIT and control) in a 1:1 ratio. Randomization will be performed using the block randomization method. Randomization will be performed using the block randomization method. A randomization list will be generated and assignments will be placed into

closed envelopes and given to each study participant. Participants will be assessed at baseline and 16-wks post HIIT or control

3 STUDY POPULATION

3.1 INCLUSION CRITERIA

1. Men and women, 19-65 years of age.
2. Confirmed diagnosis of traumatic SCI at the cervical or thoracic level (C7-T12), classified as A, B, C, or D (motor and sensory complete or incomplete) on the AIS scale.
3. At least 3 years post-injury.
4. Able to independently operate an arm ergometer.
5. Have access to a wireless internet connection.
6. Medically stable, able to provide informed consent

3.2 EXCLUSION CRITERIA

1. Cardiovascular or renal diseases.
2. Pregnant women
3. Orthopedic conditions that prevents arm ergometry
4. Upper extremity musculoskeletal conditions that prevents arm ergometry.
5. Neurological disorder that prevents arm ergometry
6. Participation in a structured exercise program currently or in the past 3 months.
7. Unable to perform exercise interventions

4 STUDY INTERVENTION

4.1 STUDY INTERVENTION(S) ADMINISTRATION

4.1.1 STUDY INTERVENTION DESCRIPTION

In a longitudinal study design, 40 participants with chronic SCI will be randomly assigned to one of the two study groups (HIIT and control) in a 1:1 ratio. Randomization will be performed using the block randomization method. Randomization will be performed using the block randomization method. A randomization list will be generated and assignments will be placed into closed envelopes and given to each study participant. Participants will be assessed at baseline and 16-wks post HIIT or control. Home-Based Telehealth Exercise Intervention will include implementation of HIIT training performed on an arm crank cycle ergometer. The teleexercise will be delivered through a custom, wireless Internet-based system that will be installed in the participant's home. The equipment within this system includes a tablet computer (Samsung Galaxy Tab 2 10.1, Samsung) with Bluetooth® and wireless Internet capability mounted to an adjustable floor stand (Standzfree Universal Stand, Standzout); wearable physiologic monitor (Bioharness 3, Zephyr) that provides real-time monitoring of heart and respiration rate data to the tablet via Bluetooth® connection; and custom-designed web application that allows physiologic data and video feed to be recorded from the tablet to a secure web-based dedicated server.

This platform allows the exercise trainer (telecoach) to monitor each participant's physiologic data in real-time (up to 5 second delay) while simultaneously video-conferencing and providing written instructions to the participant.. Telecoaches will utilize this system to provide immediate feedback regarding exercise intensity and movement quality during each exercise session. All exercise sessions will be performed on an upper body ergometer (UBE-BDP Table Top Upperbody Exerciser, Hudson Fitness). HIIT training will be delivered two times per week for 16 weeks (32 sessions). Each session will be separated by at least 24-hrs. Participants will be allowed to choose the days and times that they feel exercise will fit into their schedule. The HIIT protocol will be determined based on peak anaerobic power measures during an arm crank Wingate Cycle test. HIIT will consist of 20 minutes of exercise consisting of four minutes of arm crank exercise at 5% of peak anaerobic power followed by 30 seconds at 30% of the peak anaerobic power; this cycle will be repeated four times, ending with two minutes of recovery at 5% of peak anaerobic power. The use of percent workload is important as use of heart rate to prescribe exercise is not accurate in many individuals with SCI, as the sympathetic nervous system input is often impaired. Based on our preliminary data in which some participants had difficulty performing intervals using 50% of peak anaerobic power, this protocol will utilize a more modest 30% of peak anaerobic power exercise, which should be more feasible and achievable for all participants. This workload will still be higher than corresponding VO₂ peak workloads, thus will still elicit a high intensity interval session. The participants will be coached and monitored remotely via the telehealth system. Heart rate and respiratory rate will be monitored throughout each session.

4.2 MEASURES TO MINIMIZE BIAS: RANDOMIZATION

Randomization will be performed using the block randomization method. Randomization will be performed using the block randomization method. A randomization list will be generated and assignments will be placed into closed envelopes and given to each study participant.

5 STUDY INTERVENTION DISCONTINUATION AND SUBJECT DISCONTINUATION/WITHDRAWAL

5.1 SUBJECT DISCONTINUATION/WITHDRAWAL FROM THE STUDY

Subjects are free to withdraw from participation in the study at any time upon request.

An investigator may discontinue or withdraw a subject from the study for the following reasons:

- Significant study intervention non-compliance
- If any clinical adverse event (AE), laboratory abnormality, or other medical condition or situation occurs such that continued participation in the study would not be in the best interest of the subject

Subjects who sign the informed consent form and are randomized but do not receive the study intervention may be replaced. Subjects who sign the informed consent form, and are randomized and receive the study intervention, and subsequently withdraw, or are withdrawn or discontinued from the study, will not be replaced.

A subject will be considered lost to follow-up if he or she fails to return for 2 scheduled visits and is unable to be contacted by the study site staff.

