7.3 STATISTICAL ANALYSES

Descriptive statistics, such as means, standard deviations, and 95% confidence intervals, will be calculated for all study variables of interest. The primary method of analysis will be mixed models repeated measures analyses, such as repeated measures analysis of covariance. This will allow us to test the group, time, and group by time interaction effect simultaneously. An appropriate structure for the covariance matrix (e.g. the unstructured covariance matrix) will be selected for these models using the final data. The Tukey-Kramer multiple comparisons test will be used as the *post hoc* test of choice for these analyses. ***Biological variables, such as age, sex, race, and %fat, will be accounted for in these models (see Rigor and Reproducibility in Statistical Design and Power document for details)*** Overall comparisons between means of the two groups will be performed using the two-group t-test, and overall changes within groups will be examined using the paired t-test. Correlation analysis will be performed, with Pearson correlation coefficients being calculated for pairs of continuous variables. Distributions of continuous variables will be examined for normality using box plots, stem-and-leaf plots, and normal probability plots; those deviating greatly from a normal distribution will be log transformed or analyzed using appropriate nonparametric tests such as the Wilcoxon rank-sum and signed-rank tests. Multiple imputation methods may be used to address missing data for variables with moderate amounts of missing data ($\geq 10\%$) and after examining whether data are missing completely at random (MCAR), at

random (MAR), or not at random (MNAR). Statistical tests will be two-sided and will be performed using a 5% significance level. SAS software, version 9.4 or later, will be used to conduct the statistical analyses.

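### Section 5.1 lets randomised participants be replaced, or withdrawn from the study for non-compliance, mainly in the HIIT arm in practice, and section 7.3 names no analysis set that keeps the groups as randomised

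*Combined protocol and SAP*

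**What the plan says.** Section 5.1 contains two permissive rules.

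- Replacement: "Subjects who sign the informed consent form and are randomized but do not receive the study intervention may be replaced". The next sentence limits this: people who have received the intervention and then leave are not replaced.
- Withdrawal: "An investigator may discontinue or withdraw a subject from the study for the following reasons", and the first reason listed is "Significant study intervention non-compliance". No threshold is given. The power covers removal from the study, not only from the exercise programme.

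The synopsis (1.1) lists the comparator under the study intervention, as "Other: No-exercise control group", so both rules formally apply to both arms. Section 5.1 does not say what receiving the intervention, or failing to comply with it, would mean for a control. Under section 4.2, "assignments will be placed into closed envelopes and given to each study participant".

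On timing, section 2.1 states: "Participants will be assessed at baseline and 16-wks post HIIT or control". There is no visit in between.

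Section 7.3 makes mixed models for repeated measures the primary method and adds: "Overall comparisons between means of the two groups will be performed using the two-group t-test". On missing data: "Multiple imputation methods may be used to address missing data for variables with moderate amounts of missing data", with moderate defined as 10% or more. Neither 7.3 nor any other section names an analysis set. Nothing says whether a replaced or withdrawn person is assessed at week 16 or analysed, or how a replacement is allocated.

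**The concern.** Randomisation makes the two groups comparable at entry. That comparability carries through to week 16 only if the people compared are those who were randomised. Both rules in 5.1 act after randomisation, and both select on starting or adhering.

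The selection is unlikely to be balanced. HIIT asks for 32 coached sessions over 16 weeks, and the control asks for none. A participant can learn the assignment before deciding whether to start. Refusals to start and poor attendance are therefore mainly HIIT events. If people who do not start or adhere poorly have a worse prognosis, losing them from one arm flatters HIIT. The direction is likely but not certain, and it may differ between endpoints such as lipids and blood pressure.

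The secondary goal is also exposed. Section 1.2 gives it as uptake and implementation, and the week-16 interview in 7.1 covers influences on adherence. People who stopped are the most informative on that subject. Nothing bars interviewing them, but someone withdrawn from the study may not be reached.

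**Working it through.** **No figure to reproduce.** Section 7.2 gives 40 participants with no effect size, SD, power or dropout allowance. The calculation below is for scale only.

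**Inputs from the documents.** 40 randomised 1:1, so 20 per arm (2.1, 7.2); two-sided 5% tests, including a two-group t-test (7.3).

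**Assumed inputs.** k HIIT participants are lost through one of the rules. Their change would have been D SD worse than that of the other HIIT participants even with no treatment effect. All 20 controls are analysed, and the SD of change is 1.

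**Bias.** With no true effect, the full HIIT arm has the same mean change as control, set at 0. If a share p of the arm has mean m − D and the rest have mean m, then m − pD = 0, so m = pD. Analysing only the rest gives a bias of pD.

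- Withdrawn without replacement: p = k/20, and 20 − k are analysed in HIIT.
- Replaced within the arm: 20 + k people have been assigned to HIIT, so p = k/(20 + k), and 20 are analysed.

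**Type I error.** Noncentral t with n1 + 20 − 2 degrees of freedom and noncentrality bias / √(1/n1 + 1/20), where n1 is the number analysed in HIIT. The rejection probability is summed over both tails.

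Worked case: k = 4, D = 1.0, withdrawn. Bias = (4/20) × 1.0 = 0.20 SD; n1 = 16; noncentrality = 0.20 / √(1/16 + 1/20) = 0.596; 34 degrees of freedom; critical value 2.032; type I error 8.93%.

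| k | D (SD) | Withdrawn: bias (SD) | Withdrawn: error | Replaced: bias (SD) | Replaced: error |
|---|---|---|---|---|---|
| 1 | 0.5 | 0.025 | 5.07% | 0.024 | 5.06% |
| 1 | 1.0 | 0.050 | 5.27% | 0.048 | 5.25% |
| 2 | 0.5 | 0.050 | 5.26% | 0.045 | 5.23% |
| 2 | 1.0 | 0.100 | 6.03% | 0.091 | 5.90% |
| 3 | 0.5 | 0.075 | 5.56% | 0.065 | 5.46% |
| 3 | 1.0 | 0.150 | 7.27% | 0.130 | 6.87% |
| 4 | 0.25 | 0.050 | 5.24% | 0.042 | 5.19% |
| 4 | 0.5 | 0.100 | 5.97% | 0.083 | 5.76% |
| 4 | 1.0 | 0.200 | 8.93% | 0.167 | 8.08% |

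**A different model as a cross-check.** In 40,000 simulated trials per scenario with no true effect, the k least compliant HIIT participants were removed or replaced, and compliance had correlation rho with the outcome change. For k = 4, type I error was 6.1% (rho = 0.3) and 8.1% (rho = 0.5) when they were withdrawn, and 6.0% and 7.7% when they were replaced. At rho = 0 it stayed near 5%.

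**Would the planned analysis repair this?**

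- Mixed model: with one post-baseline visit, a person withdrawn before it supplies a baseline value and nothing on their own change.
- Two-group and paired t-tests: these use observed values only.
- Multiple imputation: optional, and considered from 10% missing. That is 4/40; losing 1 to 3 people (1/40 = 2.5% to 3/40 = 7.5%) does not reach it.

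**The case against.** The strongest reply is that nobody is excluded in writing. Both rules are permissions, 7.3 compares the two groups, and 2.1 defines those groups by random assignment. Replacement is also confined to people who never started. All of this is correct. But withdrawal from the study ends data collection unless the plan says otherwise, and the plan does not. The withdrawal rule therefore goes further than a missing label.

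Second, the asymmetry between arms is inferred. Section 5.1 is worded for both arms, a control could breach the protocol by taking up exercise, and disappointed controls may leave too. Losses in both arms could shrink the bias. This stands as a limit: the table covers HIIT losses only.

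Third, the larger figures need four losses, which is 20% of the HIIT arm and reaches the imputation threshold, and a gap in untreated change of 0.5 to 1.0 SD, which may be wide for medically stable people with chronic injury. This also stands. Below the threshold the error runs from 5.1% to 7.3%, and with D = 0.25 SD it barely moves.

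Fourth, the calculation uses the t-test and not the primary mixed model. If loss depends only on observed data, that model could reduce the bias through baseline and covariates. It would not if loss depends on the unseen week-16 outcome.

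Last, 7.3 refers to a separate rigor and statistical design document that is not among those reviewed. It is cited there for biological variables. Whether it defines an analysis set cannot be checked, but an analysis set alone would not recover outcomes that were never collected.

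**Conclusion.** The concern holds and should be fixed. Section 5.1 permits post-randomisation replacement and withdrawal tied to starting and adherence, and nothing in the plan keeps those people in follow-up or in the analysis. If the rules are used, the week-16 comparison need no longer be between the groups as randomised.

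The potential bias is modest. Four HIIT losses with D of 0.5 to 1.0 SD take the nominal 5% error to between 5.8% and 8.9% over the two routes; one or two losses leave it at 6.0% or below. These sizes rest on assumed k and D, on losses in the HIIT arm only, and on a t-test of observed values. The reading of the text does not depend on those assumptions. The reason to act now is that week-16 data not collected cannot be recovered later.

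**What to change.** Add to sections 5.1 and 7.3:

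- All randomised participants are analysed in their assigned arm.
- Any replacement is an addition that takes the next assignment on the randomisation list. The person replaced stays in follow-up and in the data set.
- Non-compliance with the intervention is not by itself a ground for withdrawal from the study. The week-16 assessment and interview are still sought unless consent is withdrawn.

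This concerns follow-up and analysis only; the grounds for stopping exercise are left as they are.

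The cost is a few sentences, a few more week-16 visits, and possibly a few participants beyond 40 (40 + 4 = 44 if four are added). The estimated effect may be smaller, because non-starters and poor adherers stay in.

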6 STUDY ASSESSMENTS AND PROCEDURES

6.1 STUDY ASSESSMENTS

Body Composition, Resting Energy Expenditure, Insulin Sensitivity, Blood Pressure, blood lipids, Aerobic Capacity, Anaerobic Capacity.

6.2 ADVERSE EVENTS AND SERIOUS ADVERSE EVENTS

6.2.1 DEFINITION OF ADVERSE EVENTS (AE)

Adverse event means any untoward medical occurrence associated with the use of an intervention in humans, whether or not considered intervention-related (21 CFR 312.32 (a)).

6.2.2 DEFINITION OF SERIOUS ADVERSE EVENTS (SAE)

An adverse event (AE) is considered “serious” if, in the view of either the investigator or sponsor, it results in any of the following outcomes:

- Death
- A life-threatening adverse event (of note, the term “life-threatening” refers to an event in which the subject was at risk of death at the time of the event, rather than to an event which hypothetically might have caused death if it were more severe)
- inpatient hospitalization or prolongation of existing hospitalization
- a persistent or significant incapacity or substantial disruption of the ability to conduct normal life functions
- or a congenital anomaly/birth defect.

Important medical events that may not result in death, be life-threatening, or require hospitalization may be considered serious when, based upon appropriate medical judgment, they may jeopardize the subject and may require medical or surgical intervention to prevent one of the outcomes listed in this definition. Examples of such medical events include allergic bronchospasm requiring intensive treatment in an emergency room or at home, blood dyscrasias or convulsions that do not result in inpatient hospitalization, or the development of drug dependency or drug abuse.

6.2.2.1 SEVERITY OF EVENT

For adverse events (AEs), the following guidelines will be used to describe severity:

- **Mild** – Events require minimal or no treatment and do not interfere with the subject’s daily activities.
- **Moderate** – Events result in a low level of inconvenience or concern with the therapeutic measures. Moderate events may cause some interference with functioning.
- **Severe** – Events interrupt a subject’s usual daily activity and may require systemic drug therapy or other treatment. Severe events are usually potentially life-threatening or incapacitating. Of note, the term “severe” does not necessarily equate to “serious.”

